4.12. Data collection on infant and child mortality

At the enrollment visit, a data collector hired by the the study team will interview a household head to collect information on household composition. S/he will record the household members in a password-protected and encrypted electronic trial database, to which s/he can refer to and which s/he will update during subsequent visits. The database will include the following information on each member of the household: Sex, name, date of birth, age, date of start of follow-up (enrollment of household or in-migration), date of end of follow-up (death, withdrawal, or out-migration)

At each of the subsequent visits, the data collector will check the vital status (alive, dead, out-migrated, or unkown) of the previously registered household members and record any new births and in-migrations. If a child death - is noticed, there will be a special set of questions on the date and cause of death. Cause of death will be classified into trauma, acute illness of less than two weeks duration, prolonged illness of more than two weeks of duration, or other, i.e. no extensive verbal autopsies or other cause of death ascertainment will be done. Valid vital status information can be obtained from a parent or other caretaker of the child who lives in the same household; if such a person is not available, the information will be considered missing.

Mortality will be expressed as deaths / 1000 years at risk. Each 3-month interval will contribute to mortality calculation. Children will be included in the analyses if they were present in the household at the beginning of the interval and their vital status (dead or alive) was known and provided to the study team at the subsequent visit, by an eligible adult (see above for eligibility criteria). Time in follow-up will be the number of days between the beginning of the interval and death, outmigration, or end of interval, whichever came first. All mortality data i.e. from both the primary outcome sample and the secondary outcome sample will be used for the primary mortality outcome analysis.

Mortality rates will be calculated separately for 29-364 days old infants (the primary target population for the intervention) and for 12.00-59.99 month old children (who have not themselves received the MDA intervention). The indicated figures refer to the subject's age at the beginning of the interval.

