4.07. Outcome variables

Primary efficacy outcome:

1. Mortality (deaths / 1000 years at risk) among children who were 1–11 month (29–364 days) old at the time of study drug administration.

2. As an exploratory analysis, we will assess the following factors as potential effect modifiers to the azithromycin impact on mortality among the 1–11-month (29–364 days) olds
 - a. Infant age at the time of MDA (1–5 months vs 6–11 months)
 - b. Infant weight-for-age, length-for-age, weight-for-length at the time of MDA
 - c. Infant sex
 - d. Season of MDA dosing (malaria versus non malaria season) and SMC implementation in village (SMC given versus SMC not given)
 - e. Cluster level coverage of SMC
 - f. Cluster level baseline mortality (established at first census)
 - g. Cluster and individual level coverage and number of administered azithromycin MDA doses
 - h. District of residence
 - i. Distance from the nearest health facility
 - j. Household asset or income index
 - k. Household WASH index
 - l. National outreach strategy category (standard/advanced)
 - m. Hard-to-reach village status assessed by the field workers

Secondary efficacy outcomes:

1. Prevalence of diarrhea, ARI, malaria, or other illnesses in the 14-day period before MDA visits
2. Mean weight-for age, length for age, weight-for-length, and mid upper arm circumference, and prevalence of moderate to severe stunting ($LAZ < -2$ / $LAZ < -3$) and moderate to severe wasting ($WLZ < -2$ / $WLZ < -3$) at 6–8 and 12–14 months of age.
3. Mortality (deaths / 1000 years at risk) among children who were 12–59-month-old when the latest azithromycin MDA took place in their village of residence.
 - a. This will be analyzed since azithromycin MDA could elicit herd protection that could theoretically extend beyond the actual recipient population of the treatment.

Outcomes related to antimicrobial resistance:

1. Phenotypic macrolide resistance among *E. coli* strains isolated from stool samples or *S. pneumoniae* strains isolated from nasopharyngeal swabs among 4–14-month-old children, at one year after the MDA intervention has stopped (36 months after baseline).
 - a. As descriptive information, we will provide the same information from a smaller group of children at baseline and when the intervention has continued for 12 and 24 months (i.e., after 4 or 8 rounds of MDA).

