4.15. Data collection on infant growth and nutritional status

A relatively recent meta-analysis suggested that antibiotic treatment of children in low-income countries might improve their linear growth (Gough et al., 2014). The review did not include enough studies on infants, so the question of antibiotic effect on infant growth is still open. It is, however, possible, that azithromycin might also promote growth in this age group (in which length and weight gain is faster than among older children), and hence it justifiable to study growth as a secondary outcome in a mortality trial.

The sub-sample will be formed from children, who reside in the 60 villages around the four selected health centers (secondary outcome sample). In these villages, data collectors will take anthropometric measurements from 6-8 and 12-14 month old children on study visits 6, 7, 8, and 9, i.e. at 15, 18, 21, and 24 months after the enrollment of the village into the trial. At these visits, the 6-8 month-old and 12-14 month old children will have received two and four doses of study drugs, respectively, unless they migrated into the village later, were absent, unlocated or declined study drug administration. Thus this sampling frame ensures maximal exposure to the study drug at size assessment.

At each time point, we expect to measure a mean of 7.5 children / village, i.e. the total sample size will be 1800 children, i.e. approximately 600 per group. This sample size will provide the study with 80% power to detect difference of approximately 0.2 SD units in anthropometric indices, which is a typical achievement in nutritional supplementation trials (Dewey and Adu-Afarwuah, 2008).

Measurements taken from the sub-sample include length, weight, and mid upper arm circumference (MUAC). Length will be assessed using a commercial length board (ShorrBoard®, WEIGH AND MEASURE, LLC, Olney, Md, USA) and recorded to the nearest 1 mm. Weight will be assessed using an electronic infant weighing scale (SECA 354) with reading increments of 10g. MUAC will be measured with non-stretchable plastic insertion tapes and the results will be recorded to the nearest 1 mm. All measurement will be done in triplicate.

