10. Quarterly azithromycin MDA to 1-11 month (29-364 days) old infants does not increase carriage of azithromycin resistance bacteria in treated infants 1 year after

their treatment has stopped, who live in a village where MDA intervention has also ceased.

- a. Measured after the intervention for individual child has stopped for 1 year
- b. Separately, there is a similar hypothesis on the effect of biannual azi MDA

11. Quarterly azithromycin MDA to 1-11 month (29-364 days) old infants does not increase carriage of azithromycin resistance bacteria in treated infants 1 year after their treatment has stopped, who live in a village where MDA intervention has continued.

- a. Measured after the intervention for individual child has stopped for 1 year
- b. Separately, there is a similar hypothesis on the effect of biannual azi MDA.

The study hypotheses in terms of azithromycin mechanism of action are the following:

12. Azithromycin MDA reduces malaria prevalence and parasite density, and improves mean blood hemoglobin concentration among 4–11-month-old infants, within 14 days of the MDA
 - a. For these analyses, the two azithromycin can be combined
13. Azithromycin MDA reduces general inflammation (CRP) among 4–11-month-old infants, within 14 days of the MDA
 - a. For these analyses, the two azithromycin can be combined
14. Azithromycin MDA reduces intestinal inflammation (fecal neopterin, myeloperoxidase, and alpha-1-antitrypsin concentrations) among 4–11-month-old infants, within 14 days of the MDA
 - a. For these analyses, the two azithromycin can be combined

There is no predefined hypothesis about the impact of biannual or quarterly azithromycin MDA to 1–11-month-old infants on mortality among 12–59-month-old children living in the same communities, but we will measure group-level differences on this as exploratory analysis.

There are also no predefined hypotheses about the feasibility, acceptability, or equity of the azithromycin MDA intervention.

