5.02. Analytical approach

The study team will express mortality in the three groups as number of deaths per 1000 person-years at risk (deaths/PYR) and AMR as the proportion of *E. coli* or *S. pneumoniae* isolates that have reduced susceptibility (R or I category) towards azithromycin. For pairwise comparisons between any of the two groups, the team will calculate incidence rate ratio and its 95% confidence interval (CI) for mortality and risk ratio and its 95% CI for AMR prevalence at 12 and 24 months after the onset of the azithromycin MDA intervention.

As an exploratory analysis, the team will also assess mortality (deaths / 1000 years at risk) among children who were 12–59-month-old at the time of the previous study drug administration in their village of residence. There is no predefined hypothesis for this

analysis, but it can provide information about possible herd protection generated through targeted azithromycin MDA.

Mixed-effect Poisson regression model will be used to estimate the intervention effects on mortality, with random intercepts for the clusters. For twins, no adjustment for interdependence will be made, i.e. we plan to analyse the data assuming independence between infants from the same mother. This is because our previous methodological research has demonstrated that analytic models that assume independence are robust in situations where cluster size is small and only a few of the analysable units are clustered (such as 1-2% twin rate, Xu et al., 2014). As per the closed-testing method for controlling multiplicity arising from multiple group comparisons, global null hypothesis of mortality in all three groups being the same will be tested at 5% significance level. Pairwise null hypothesis can be rejected only if the global null hypothesis has been rejected. Pairwise incidence rate ratio and corresponding 95% confidence intervals will be estimated.

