The relative risk reduction (RRR) of 20% in the azi-biannual group is modelled on the MORDOR-trial, in which the point-estimate for mortality reduction among under-one-year old infants was 25% (in all the study countries) (Keenan et al, 2018). We estimate this reduction be slightly lower in Mali, because of the seasonal malaria chemoprevention that will be offered to 3-11-month-old infants in the Mali but was not practiced at the MORDOR sites. The 40% RRR for the azi-quarterly group is also modelled on MORDOR result indicating that in that sample practically all the mortality effect was concentrated in the first 3 months after the MDA (Porco et al, 2019).

For the AMR data collection, the sample size will be 60 clusters or 1,350 children per time-point. This number will be tested from 4–14-month-old children at 12 months after the intervention has stopped and from 49–59-month-old children when 8 rounds of MDA have been completed. At the three other time points, we will test 450 children (taken

randomly from 20 clusters / arm). In total, this will mean 5,400 AMR-analyses for *S. pneumoniae* and the same number for *E. coli*.

The AMR sub-sample size is based on the following assumptions

1. 95% *E. coli* and 65% *S. pneumoniae* recovery rate from the collected samples
2. AMR prevalence of 12% in the control group for *E. coli* and 6% for *S. pneumoniae*. These figures come from analysis of azithromycin resistance in 50 *E. coli* and 50 *S. pneumoniae* samples from Mali in the so called ABCD trial.
3. Non-inferiority margin of 10%-points in AMR prevalence
4. 80% power, one-sided 2.5% type 1 error rate for each pairwise comparison against placebo control
5. Coefficient of variation of 0.3 in AMR among clusters.

For the analyses on azithromycin mechanism, we are using a convenience sample, i.e. all available children in the intended age-brackets (and avoiding repeated venous blood collection from the same children), in the study clusters where the AMR work is done. The sample size of 1,000 – 1,350 / analysis, or a mean of 333 - 450 / intervention arm, will provide these analyses 80% power at 5% two-sided type 1 error rate to detect an effect size of 0.25 – 0.30, assuming an intra-cluster correlation coefficient of 0.03 and a design effect of 1.6 to 2.

For intra-household analyses there are no pre-set hypotheses, but the data will be used for descriptive purposes.

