6.04. Amount of collected blood and other biospecimens

From most participants, there will be no biological specimen collection.

At four time points, for a sub-sample of approximately 1,350 4-14 month old children and the same number of 49-59 month old children, we will also collect rectal and nasopharyngeal or rectal swabs. At each time point, the children will be different, so for each child, there will only be one sampling. Additionally, at visit 11 we will sample 15-26-months old children who have received 1-4 doses of MDA 1 year earlier in villages that have stopped MDA. In the Koulikoro or Kati (tertiary AMR sample) region we will sample 24-35 months old children who have received 1-4 doses of MDA 1 year earlier and who live in a village that has continued MDA. This will allow us to assess whether azithromycin resistant bacteria survive in individuals that have previously been treated. We will use flocculated swabs for the nasopharyngeal and stool samples. The estimated mass of the collected stool is 200 ug.

From a subgroup of 6-8-month-old or 12-14 month old infants and young children, there will be one venous blood collection, with a total collected blood volume of maximum of 5 ml. The collected volume represents approximately 1% of the infant's total blood volume and it is replaceable from the infants' own blood production within 24 hours. From the same individuals, we will collect 2-10 g of stool and 5-10 ml of urine

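### Section 4.12 describes 12–59-month-olds as not having received MDA, but about a fifth of their person-time comes from children age-eligible for study drug earlier, so this exploratory comparison alone cannot separate herd protection from carry-over

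*Combined protocol and SAP*

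**What the plan says.** Section 4.12 plans separate mortality rates for infants aged 29–364 days and "for 12.00-59.99 month old children (who have not themselves received the MDA intervention"). It adds: "The indicated figures refer to the subject's age at the beginning of the interval". Group membership is therefore reassessed at every interval.

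Section 4.07 (secondary efficacy outcome 3) defines the older group only by age at the latest MDA in the village, and justifies the analysis because "azithromycin MDA could elicit herd protection that could theoretically extend beyond the actual recipient population of the treatment". Section 5.02 says of the same analysis that "it can provide information about possible herd protection generated through targeted azithromycin MDA". Its status is exploratory in 4.02 (question 1.5) and 5.02, and 5.01 states: "There is no predefined hypothesis about the impact of biannual or quarterly azithromycin MDA to 1–11-month-old infants on mortality among 12–59-month-old children".

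Other sections treat some children over 12 months as past recipients:

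- Section 4.15, on visits 6 to 9: "the 6-8 month-old and 12-14 month old children will have received two and four doses of study drugs". It allows for late in-migration, absence and refusal. Section 4.17 gives 3–4 doses for the 12–14-month-olds.
- Section 6.04, on the tertiary AMR sample, which 4.07 and 4.16 place at visit 9: "we will sample 24-35 months old children who have received 1-4 doses of MDA 1 year earlier".
- Section 4.07, for the AMR outcomes, names 49–59 months as the age band that never receives azithromycin over a two-year MDA period.

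**The concern.** Infants aged 29–364 days are dosed every 3 months for up to eight rounds (4.05, 4.06). A resident child who turns 12 months after the village's first round was age-eligible at least once, yet from then on counts as a child who has not received the MDA. If the parenthesis in 4.12 was meant as a restriction to untreated children, no rule for applying it is written. The number-of-doses effect modifier in 4.07 applies only to the 1–11-month-olds.

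Exposure to azithromycin among these older children differs by arm. In control villages earlier doses were placebo. In azi-quarterly they were azithromycin. In azi-biannual they were azithromycin at January–June visits and placebo at July–December visits. A difference in the 12–59-month rate could therefore reflect protection of untreated children, a lasting effect in treated ones, or both. A reader who relies on 4.12 would take all of it as an effect in children who were never treated.

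**Working it through.** **Inputs.** Eligibility at 29–364 days (4.05). Visits every 3 months, MDA at the first eight (4.06). 50% of clusters with 8 rounds, 30% with 7, 20% with 6, and 34 of 39 infants dosed per round (5.04). *Assumptions:* ages uniform over 12–59 months (48 months wide), no migration, pilot-interval exclusions ignored.

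**Follow-up weights, checked against the plan.** 6 × 35,650 + 28,520 + 17,820 = 260,240, against approximately 260,200 stated in 5.04. Since 0.8 × 35,650 = 28,520 and 0.5 × 35,650 = 17,825, the weights for intervals 1–8 are 1, 1, 1, 1, 1, 1, 0.8, 0.5 (sum 7.3).

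**Share age-eligible earlier.** Interval k starts t = 3(k − 1) months after village entry. With 3-month spacing, a resident child aged 12 months or more at that point was age-eligible at an earlier round if younger than 12 + t. Share = t/48.

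| Interval | 1 | 2 | 3 | 4 | 5 | 6 | 7 | 8 |
|---|---|---|---|---|---|---|---|---|
| t (months) | 0 | 3 | 6 | 9 | 12 | 15 | 18 | 21 |
| Share (%) | 0 | 6.3 | 12.5 | 18.8 | 25.0 | 31.3 | 37.5 | 43.8 |

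Weighted sum of t: 3 + 6 + 9 + 12 + 15 + 0.8 × 18 + 0.5 × 21 = 69.9. Weighted share: 69.9 / (48 × 7.3) = 69.9 / 350.4 = **19.9%**. With eight rounds everywhere it is 21.9%. If numbers of children fall 2–10% per year of age, it is about 20–23%.

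Within 12–23 months the share is min(t, 12)/12: (0.25 + 0.5 + 0.75 + 1 + 1 + 0.8 + 0.5) / 7.3 = 4.8 / 7.3 = **65.8%**.

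**Actually dosed with study drug.** Coverage c = 34/39 = 0.872.

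- Same children always missed: 19.9% × 0.872 = 17.4%.
- Misses independent between rounds: the 69.9 splits into 18.9 with one earlier eligible round, 15.9 with two, and 35.1 with three or four. Then (18.9 × 0.872 + 15.9 × 0.984 + 35.1 × 0.998) / 350.4 = 19.2%.

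**Actually dosed with azithromycin.** Control 0%. Azi-quarterly 17–19%. For azi-biannual, count the months of age, from 12 upward, that were eligible at a January–June round:

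- January–March or April–June start: same as the table, 19.9%.
- July–September start: 0, 0, 0, 3, 6, 9, 12, 15 months; weighted 35.1 / 350.4 = 10.0%.
- October–December start: 0, 0, 3, 6, 9, 12, 15, 18 months; weighted 51.0 / 350.4 = 14.5% (14.6% before allowing for the exact eligibility limits in days).

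After coverage these run from 8.7% (10.0% × 0.872) to 18.8% (January–March start, independent misses).

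**Share of deaths.** Previously eligible children are aged 12 to 33 months. If mortality at 12–35 months is m times that at 36–59 months (assumption), their share of deaths is 0.199m / (0.5m + 0.5): 26.6% for m = 2 and 29.9% for m = 3.

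**Illustration with no herd effect.** Suppose a lasting rate ratio of 0.80 in all previously eligible children. The 12–59-month rate ratio would be 1 − 0.199 × 0.20 = 0.960 by person-time, or 1 − 0.266 × 0.20 = 0.947 and 1 − 0.299 × 0.20 = 0.940 by deaths. This is an upper case that fits azi-quarterly. At the lowest azi-biannual recipient share it is 1 − 0.087 × 0.20 = 0.983. If the benefit ends 3 months after a dose, the ratio is close to 1.00.

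**The case against.** **Another reading of the parenthesis.** The outcome unit is the 3-month interval, so the words could mean not dosed at the round that opens the interval, which is always true. This strains the text, which says without qualification that the children have not received the intervention. If it is what was meant, it needs saying.

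**Carry-over should be small by design.** A child aged 12 months or more at the start of an interval had any last dose about 3 months earlier or more, and section 5.04 cites earlier data in which "practically all the mortality effect was concentrated in the first 3 months after the MDA". This stands: on the plan's own model the bias is near zero. But the plan also looks for effects beyond that window, such as growth and measles-vaccine response at 12–14 months and resistance carriage a year after treatment, so carry-over cannot be ruled out in advance.

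**Nothing confirmatory depends on it.** This also stands. The wording in 4.07 and 5.02 is tentative, and the comparison of all 12–59-month-olds answers question 1.5 validly as an overall community effect.

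**The herd-protection subset has a cost.** At round 8 it loses 44% of person-time and contains only children aged 33 months or more, just when a cumulative herd effect might be largest. It therefore describes an older population. That is a reason to keep the overall rate beside it.

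**Conclusion.** The concern holds. The description in 4.12 is wrong after a village's first interval and conflicts with 4.15, 4.17 and 6.04. About 20% of 12–59-month person-time, and about two thirds of that at 12–23 months, comes from children age-eligible for study drug earlier. This rests on uniform ages and no migration; in-migration would lower it somewhat, and a younger age mix would raise it slightly. The primary mortality analysis is unaffected, and the randomised comparison in older children remains valid as an overall effect. What cannot be supported as written is its reading as herd protection in children outside the treated group. The distortion is probably small, but the plan gives no way to check that. It should be corrected.

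**What to change.** 1. In 4.12, delete the parenthesis or replace it with a statement that, after a village's first interval, the group includes children who were age-eligible for study drug at earlier rounds.
2. Keep the all-12–59-month rate and label it the overall community effect (question 1.5).
3. In 4.07 (secondary outcome 3) and 5.02, base the herd-protection reading on children already 12 months or older on the date of the village's first MDA visit. Define this by age-eligibility and not by receipt, so that the randomised comparison is kept.
4. Report previously age-eligible 12–59-month-olds separately.

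The cost is wording in three sections and one derived variable from birth and visit dates already recorded. The herd-protection subset gives up about 20% of person-time overall, and about 27–30% of deaths under the mortality assumption above. Classifying by age alone also places some in-migrants who were never dosed in the previously eligible group.
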